## II. STUDY OBJECTIVE(S); INCLUDING SPECIFIC AIMS AND/OR HYPOTHESES

The primary objective of this study is to determine if there is any difference in the length of stay between patients with shoulder dislocation who are treated with traditional x-ray imaging for diagnosis and reduction confirmation and those that are treated with POCUS for diagnosis and reduction confirmation.

*Hypothesis:* The use of POCUS for shoulder dislocation and reduction confirmation will reduce the length of stay for ED patients.

The secondary objectives of this study include evaluating patient satisfaction, providing a cost analysis, time to diagnosis, confirmation of reduction, and volume of x-ray reduction.

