## III. METHODS

This study is a prospective, randomized, non-blinded evaluation of the use of ultrasound to diagnosis shoulder dislocation in emergency departments. The study population will consist of patients aged 18-65 that present to the VCU Emergency Department between August 1, 2020 and December 31, 2022 with suspicion of an uncomplicated shoulder dislocation.

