### Procedural Overview/Design:

1. Assess patient for enrollment. Apply inclusion and exclusion criteria (below).
2. Discuss Informed consent with patient. If patient consents, proceed to step 3.
3. Randomize patient with premade numbered envelopes stating standard of care or ultrasound protocol (description below).

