##### Study Procedure Data

Group assignment (control or experimental)  
Experience of person performing ultrasound if in experiment group  
Minimal: Minimal prior experience, sufficient training completed  
Moderate: Prior shoulder ultrasound experience  
Expert: Fellowship trained, or significant prior exposure

Type of sedation/block/analgesic given  
Intra-articular? Nerve block? Procedural sedation?

Technique of shoulder reduction performed

Number of x-rays ordered

If ultrasound group, what x-ray was ordered and why  
Portable?

Findings

Type of dislocation (anterior versus posterior)

Fractures identified  
Missed diagnoses

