#### B. Statistical Methodology

Descriptive statistics will be used to evaluate demographic variables. Categorical variables will be reported as n (%) and will be analyzed by chi-square or Fisher's exact test as appropriate. Normally distributed continuous variables will be reported as mean and standard deviation and will be analyzed by student's t-test. Non-normally distributed continuous variables will be reported as medians and interquartile range and analyzed using Mann-Whitney U test. The primary outcome of difference in average length of stay in the ED will be analyzed by paired students T-test. Secondary outcomes will be evaluated by paired student t-tests as well. Statistical analysis will be performed using SPSS® Software (version 24; 2016) and the level of significance set at p value less than 0.05.

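### A paired t-test is prescribed for the primary and secondary outcomes, but the two arms are independent randomised patients with no pairs

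*Combined protocol and SAP*

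**What the plan says.** The combined protocol and SAP describes the trial in Section III as follows: "This study is a prospective, randomized, non-blinded evaluation of the use of ultrasound". Step 3 of the Procedural Overview reads: "Randomize patient with premade numbered envelopes stating standard of care or ultrasound protocol". Section IV (Study Procedure Data) records one group, control or experimental, for each patient. The primary objective in Section II is to "determine if there is any difference in the length of stay between patients with shoulder dislocation who are treated with traditional x-ray imaging" and those managed with point-of-care ultrasound. That is a contrast between two sets of patients.

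Section V.B then prescribes the tests. For the primary outcome: "The primary outcome of difference in average length of stay in the ED will be analyzed by paired students T-test". For the rest: "Secondary outcomes will be evaluated by paired student t-tests as well". Earlier in the same paragraph, chi-square or Fisher's exact test is given for categorical variables and Student's t-test (not called paired) for normally distributed continuous variables. For the remaining continuous variables it says: "Non-normally distributed continuous variables will be reported as medians and interquartile range and analyzed using Mann-Whitney U test".

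Section V.A gives no sample size, SD, target difference or power. The plan states neither an allocation ratio nor a block size.

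**The concern.** A paired t-test analyses within-pair differences. It suits a patient measured under both strategies, or patients matched before randomisation. This trial has neither.

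The data will hold one length of stay and one group label per patient. A paired test can be run only after someone has put control and ultrasound patients side by side in some order. That order is arbitrary, the plan does not fix it, and in a non-blinded trial it could be chosen with the results in view. Patients without a partner would drop out of the primary analysis.

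The secondary sentence makes no exceptions. Its outcomes include 1-to-5 satisfaction ratings and numbers of x-rays, for which a t-test of any kind is a poor default. An analyst who reads the earlier part of the paragraph as covering outcomes would find different tests there, all suited to independent groups.

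**Working it through.** **Is there any pairing?** Sections II, III and IV were read for a matching variable, a crossover, a before-after contrast or a patient imaged under both strategies for the primary comparison. None is described. Allocation is by individual envelope, and each patient belongs to one group.

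**Is there a figure to reproduce?** No. Everything below rests on assumptions, with two-sided α = 0.05 because sidedness is not stated.

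**Why the p-value depends on row order.** For arms of equal size n with a common SD s and observed difference D:

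- Independent test: t = D / (s√(2/n)), df = 2n − 2.
- Paired test: t = D / (s√(2(1 − r)/n)), df = n − 1, where r is the correlation that the row order happens to produce.
- Hence t(paired) = t(independent) / √(1 − r).

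Under random ordering r has mean 0 and SD 1/√(n − 1). With n = 20 that SD is 1/√19 = 0.229, so r lies within about ±1.96 × 0.229 = ±0.45.

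Suppose the independent test gives exactly p = 0.05, so t = 2.024 on 38 df:

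- r = +0.45: t = 2.024/√0.55 = 2.73 on 19 df, p = 0.013.
- r = 0: t = 2.024 on 19 df, p = 0.057.
- r = −0.45: t = 2.024/√1.45 = 1.68 on 19 df, p = 0.109.

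Simulation agrees. One dataset per size was scaled to an unpaired p of 0.05 and re-paired 3,000 times:

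| n per arm | Central 95% of paired p | Row orders with p < 0.05 |
|---|---|---|
| 20 | 0.014 to 0.108 | 39% |
| 30 | 0.017 to 0.099 | 41% |
| 50 | 0.025 to 0.083 | 42% |

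**How often the verdict is at risk.** The assumptions are lognormal length of stay, mean 240 minutes, coefficient of variation 0.45 and 20 per arm. A dataset counts as order-dependent if at least 2.5% of row orders give the opposite verdict.

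- True difference 60 minutes: about 29% to 35% of datasets across repeated simulations. The chance that one arbitrary order gives the minority verdict is about 7%.
- True difference 30 minutes (the only length-of-stay effect the protocol cites, in Section I): about 20% and 4%.

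**Lost patients.** Under simple 1:1 allocation (an assumption), the number without a partner is |n1 − n2|:

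| Total N | Chance of unequal arms | Mean number without a partner |
|---|---|---|
| 40 | 87% | 5.0 |
| 60 | 90% | 6.2 |
| 100 | 92% | 8.0 |

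**Degrees of freedom.** They fall from n1 + n2 − 2 to min(n1, n2) − 1. With 10 per arm this is 18 to 9, and the critical t rises from 2.10 to 2.26.

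**Error rates with arbitrary pairing.**

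- Type I error with normal data: 0.049 to 0.051 for the paired test.
- Power with equal arms and normal data, paired against independent: 0.364 against 0.398 (10 per arm, standardised difference 0.8); 0.672 against 0.698 (20 per arm, 0.8); 0.848 against 0.860 (30 per arm, 0.8).
- Power with arms of 25 and 35, lognormal data, a 60-minute shift and SD 240 × 0.45 = 108 minutes in both arms: 56% with Welch, 49% paired.

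**The case against.** The strongest reply is that the word paired is a slip. With one length-of-stay column and one group column, the software cannot run a paired test until somebody constructs pairs, so the analyst would probably run the unpaired test and none of the harm would occur. That is plausible. But the word appears in both outcome sentences, nothing elsewhere in the document corrects it, and running a different test would then be an undocumented departure from the plan in a non-blinded trial.

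Several limits on the size of the problem stand:

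- When pairing is unrelated to outcome, type I error is preserved on average.
- With equal arms the power loss is small.
- Patients are lost only if the arms have unequal numbers of analysable patients. Blocking would reduce this but not rule it out, since Section VII itself anticipates missing data.
- The 25-against-35 split is on the unfavourable side. Under simple allocation of 60 patients, a gap of 10 or more arises in about 25% of trials.
- The p-value ranges describe results near the threshold. A clear result would survive most row orders.

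Two points of reading also stand. The general rules in Section V.B follow a sentence about demographic variables and may be meant only for those, so the conflict is an ambiguity to resolve rather than a certain contradiction. Confirmation of reduction, a secondary objective, appears in Section IV under the ED timeline and may be a time rather than a yes/no result. Cost analysis is also listed as a secondary objective, but Section IV says it is not needed.

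**Conclusion.** The concern holds. The only prespecified test of the primary hypothesis does not fit the design, and the same test is extended to the secondary outcomes. This follows from the text alone and needs no numerical assumption.

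The practical harm is a primary p-value that is not unique. Near the threshold, with 20 to 50 patients per arm, it can fall on either side of 0.05 according to row order. Degrees of freedom are roughly halved, and patients are lost whenever the arms are unequal. The frequencies and power figures depend on the assumed distribution, effect and allocation, because the plan supplies no SD, sample size or ratio. The correction should be made before any outcome data are analysed.

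**What to change.** Replace the two outcome sentences in Section V.B.

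- **Primary:** compare length of stay between the randomised groups with an independent-samples t-test, preferably Welch, or a linear model with a term for arm. Report the mean difference with its 95% confidence interval, and state that the test is two-sided if that is intended.
- **Secondary:** choose the test by variable type from the independent-groups tests the paragraph already names: Mann-Whitney U for satisfaction ratings and x-ray counts, t-test or Mann-Whitney U for times, chi-square or Fisher's exact for any binary outcome. Say whether confirmation of reduction is a time or a yes/no result, and that the general rules apply to outcomes as well as demographics.

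Two additions are advisable but separate from the defect. One is to state that patients are analysed by assigned group, whatever imaging they finally received. The other is to add a Mann-Whitney or log-scale sensitivity analysis, because length of stay is usually right-skewed.

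The cost is two rewritten sentences, with no new data, patients or procedures.

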## **I. BACKGROUND AND SIGNIFICANCE**

The shoulder joint is the most common joint requiring reduction by emergency physicians, accounting for almost 50% of all major joint dislocations. This presentation amounts to roughly 200,000 emergency department visits each year. The estimated incidence of shoulder dislocations in the United States is 23.9 per 100,000 person/year with male gender and young age being the two largest risk factors. The current standard of care for this presentation is to identify the dislocation on both physical exam and X-ray and then confirm the success of reduction by physical exam and X-ray following reduction. X-ray imaging does expose the patient to radiation, although minimally when as compared to other radiation-based imaging. However it is now being recommended by one study that pre and post-reduction X-rays can be omitted to help decrease the length of stay, radiation exposure and overall cost. The recommendation is that X-ray can be replaced with the application of ultrasonography. The aim of this study is to further assess the efficacy of point of care ultrasonography to diagnose and gauge the reduction success of shoulder dislocations in an emergency department setting.

With increasing availability and utilization of ultrasound, multiple studies suggest that this imaging modality can play an integral role in the diagnosis of and reduction confirmation for shoulder dislocations. Studies assessing accuracy of diagnosis deemed ultrasound to be 100% specific and 100% sensitive. A recent meta-analysis concluded that ultrasound is highly sensitive and specific for shoulder reductions, dislocations, and associated fractures. Another study identified that diagnostic radiographs increased patient length of stay by 30 minutes. The ease, efficacy, and timeliness of ultrasound has the potential to decrease the length of stay for emergency department patients. A WJEM systematic review recommended that “while the data is supportive of the use of ultrasound for the diagnosis of shoulder dislocation, further studies are needed prior to routine implementation. Future studies should compare the different techniques to determine which is most

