##### Past Medical History

Prior shoulder dislocations

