## V. DATA ANALYSIS

#### A. Sample Size Considerations

1. This study will be a multicenter study. Due to the infrequent nature of this injury, the data collection phase will take place over several years.

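### The primary length-of-stay test uses no covariates, and is named as paired, although age and prior dislocation are collected and could be adjusted for at little cost

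*Combined protocol and SAP*

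**What the plan says.** Section III describes two randomised groups: "This study is a prospective, randomized, non-blinded evaluation of the use of ultrasound to diagnosis shoulder dislocation in emergency departments". The procedural overview allocates each patient from numbered envelopes and mentions no matching or stratification.

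Section IV lists age under Demographics and "Prior shoulder dislocations" under Past Medical History. The Timeline in ED list holds durations and intervals, such as ED LOS, LOS after being roomed and time to discharge. It does not list arrival date, hour or shift.

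Section V.B gives baseline variables a descriptive role, "Descriptive statistics will be used to evaluate demographic variables", and then specifies the primary test: "The primary outcome of difference in average length of stay in the ED will be analyzed by paired students T-test". It contains no regression, ANCOVA or stratified analysis. Significance is set by "the level of significance set at p value less than 0.05", with no statement of one or two sides.

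Section V.A gives no sample size, SD, target difference or power. On accrual it says: "Due to the infrequent nature of this injury, the data collection phase will take place over several years".

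**The concern.** Two things in the primary-analysis sentence do not use the design or the data well.

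- **No covariates.** Whether this is a first or a recurrent dislocation, and the patient's age, are settled before the envelope is opened, and both could plausibly relate to time spent in the ED. Left out of the model, whatever they explain stays in the error term. The plan itself calls the injury infrequent, so patients are hard to come by and precision from data already collected is worth having.
- **Paired test on independent arms.** A paired t-test needs a rule that links each patient in one arm to one in the other, and equal numbers in the arms. The protocol supplies neither, so the analysis as written cannot be carried out without an arbitrary choice.

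At stake is the width of the confidence interval for the length-of-stay difference, and whether the primary analysis is fully determined before data are seen.

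**Working it through.** The plan states no sample size, SD, power or effect, so there is no figure of its own to reproduce. Everything below except the 30 minutes is an assumption.

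**Inputs**
- Difference: 30 minutes, the only length-of-stay figure in the documents (section I: "Another study identified that diagnostic radiographs increased patient length of stay by 30 minutes"). It comes from a cited study and is not a stated design target.
- SD of length of stay: assumed 60 or 120 minutes.
- R² of the covariates for length of stay: assumed 0 to 0.30.
- Two-sided alpha 0.05 and 1:1 allocation: assumed.

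**Step 1. Gain before any cost.** Adjusted SE / unadjusted SE = sqrt(1 - R²). The equivalent increase in patients is 1/(1 - R²) - 1.

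| R² | SE factor | Equivalent extra patients |
|---|---|---|
| 0.02 | 0.990 | 2% |
| 0.05 | 0.975 | 5% |
| 0.10 | 0.949 | 11% |
| 0.20 | 0.894 | 25% |
| 0.30 | 0.837 | 43% |

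**Step 2. Cost of estimating k covariate terms.** With N patients in total, the variance is inflated by about 1 + k/(N - k - 3). Setting (1 - R²) × [1 + k/(N - k - 3)] = 1 gives a break-even R² of k/(N - 3).

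- Age and prior dislocation, k = 2: 2/57 = 0.035 at N = 60; 2/97 = 0.021 at N = 100.
- A longer list that adds day/evening/night (2 terms) and calendar half-year, k = 8: August 2020 to December 2022 touches five half-years, hence 4 terms. Break-even is 8/57 = 0.14 at N = 60 and 8/97 = 0.08 at N = 100.

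**Step 3. Net effect with k = 2.** SE factor = sqrt{(1 - R²) × [1 + 2/(N - 5)]}.

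| R² | N = 60 | N = 100 |
|---|---|---|
| 0 | 1.018 | 1.011 |
| 0.05 | 0.992 | 0.985 |
| 0.10 | 0.966 | 0.959 |
| 0.30 | 0.852 | 0.845 |

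If the covariates predict nothing, the SE rises by 1% to 2%. At R² = 0.10 it falls by 3% to 4% net.

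**Step 4. Power for a 30-minute difference.** Noncentral t, with the step 2 cost for k = 2 included.
- SD 120, 100 per arm: 42.1% unadjusted; adjusted 41.7% (R² = 0), 45.4% (0.10), 49.9% (0.20), 55.2% (0.30).
- SD 60, 63 per arm: 79.5% unadjusted; adjusted 78.9% (R² = 0), 82.9% (0.10), 87.0% (0.20), 91.0% (0.30).

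**Step 5. The paired test.** In 40,000 simulated trials with independent arms paired arbitrarily and a true effect of 0.5 SD, power was 32.2% (paired) against 33.6% (independent) at 20 per arm, and 78.9% against 79.6% at 63 per arm. Type I error was near 5% for both. So the numerical loss is small. The main problem is that no pairing exists, and unequal arms could not be analysed without dropping patients.

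**The case against.** The strongest reply is that an unadjusted comparison of randomised arms is valid. It is unbiased and keeps its type I error, and chance imbalance is already reflected in its standard error. That stands in full. A reader might infer that leaving out covariates biases the result, because imbalances are common. For example, if 40% of patients had a prior dislocation (assumed) and there were 50 per arm, the arms would differ by 10 points or more in about 36% of trials (exact binomial). Such imbalance is part of the sampling variation that the test allows for, so nothing in the documents supports a claim of bias.

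A reader might also infer that the precision is free and that arrival time can be added from data already abstracted. Neither holds. Arrival time is not a listed field. A timestamp presumably underlies ED LOS in the record, but that is inference, and the field would have to be added. Nor is adjustment free: with eight terms, an R² of 0.10 would lose precision at 60 patients in total. With two terms the cost is small.

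The documents also give no R², so the gain could be negligible. That stands too, and it limits the claim to a likely improvement of unknown size.

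Finally, V.B provides a rank test for non-normal continuous variables, and length of stay may be skewed. But the primary sentence concerns a difference in averages and names a t-test, and linear regression estimates that same mean difference.

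**Conclusion.** The point holds as a modest recommendation. The primary analysis ignores two collected variables that are fixed before randomisation, and it names a test that does not fit independent arms. The pairing is an error of specification and needs correcting whatever is decided on covariates.

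The adjustment is an efficiency gain. Under the step 2 approximation with two covariates, the standard error changes from about 2% worse (R² = 0, 60 patients) to about 15% better (R² = 0.30). The break-even R² is about 0.035 at 60 patients and 0.02 at 100. Where the trial falls in this range cannot be determined, because the documents give no R², SD or sample size.

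**What to change.** Replace the primary-analysis sentence in V.B with wording to this effect: ED length of stay will be analysed by linear regression on randomised arm, adjusted for age (continuous) and prior shoulder dislocation (yes/no), and the adjusted mean difference will be reported with its 95% confidence interval. Then:

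- Fix the covariate list before data are seen, and do not choose covariates from baseline p-values.
- Exclude anything that arises after randomisation, such as sedation, reduction technique or number of x-rays.
- Keep an unadjusted independent-samples comparison as the supporting result.
- Add arrival period only if the arrival timestamp is put on the section IV list, and code it with few terms.
- State how a missing covariate value is handled, so that no randomised patient drops out of the model. Section VII already expects some incomplete fields.
- Remove the pairing from the secondary-outcome sentence at the same time.

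The cost is a few lines of SAP text, one regression in SPSS and two degrees of freedom. Age and prior dislocation need no new data; arrival period would need one added field.

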### VI. DATA AND SAFETY MONITORING PLAN (if applicable)

This data will be stored behind the VCU firewall and on Redcap and if any transfer of data is necessary this will be done on RedCap. Once the data is collected the data will be de-identified for analysis.

### VII. STUDY LIMITATIONS

Potential selection bias based on the inclusion/exclusion criteria may reduce external validation. Theoretical user error could cause misinterpretation in ultrasound findings; this is a low risk, and has built in protection. It may be a challenge to get IRB approval across all institutions Missing data or incomplete data for specific fields may also present error.

### VIII. ETHICAL CONSIDERATIONS

#### A. *Informed Consent (Applies to studies using human subjects)*

Only patients who are able to provide written consent will be included. Those patients who are able to provide consent will be provided a brief explanation of the study and given the opportunity to ask questions, and ultimately provide or decline written consent.

Ultrasound is a common modality used to evaluate minor musculo-skeletal issues in routine patient care in the emergency department and poses no harm to patient as it uses no ionizing radiation. The conduct of this research will present no more than minimal risk to the patient.

